### **1.1.3 Treatment & goal of treatments**

Nasal continuous positive airway pressure (CPAP), the standard treatment for OSA in non-pregnant population. CPAP has been shown to reduce cardiovascular mortality, morbidity, and blood pressure [22-25]. However, there are limited data regarding the efficacy of CPAP treatment in pregnancy. CPAP also has been proposed as the adjunct therapy for pre-eclampsia [26]. Despite the safety use of CPAP in pregnant women, the results regarding improvement of pregnancy outcome were lacking [27]. Extrapolation of treatment effect of CPAP from other population may not apply to pregnancy given a different physiology during pregnancy and the effect on the fetus.

We performed a systematic review in search of the existing studies concerning the efficacy of CPAP treatment for SDB during pregnancy. Of the 7 studies included (n=111), only 3 studies were randomized controlled trials (RCT), and the other 4 studies were experimental studies with pre-post design. And of the 3 RCTs, only 1 study initiated CPAP during 1st trimester and throughout pregnancy, the other 2 RCTs applied CPAP for only 1 night.

Significant results for CPAP efficacy regarding BP-lowering effects were reported in 2 studies with the early pregnancy and long-term use, and 2 studies with 1-night use of CPAP in the pre-eclamptic women during 3rd trimester, while 1 study in gestational hypertension women with 1-night use of CPAP showed no treatment effect.

Data on pregnancy outcomes were reported in the 3 long-term early CPAP use studies. While CPAP use seemed to prevent the incidence of preeclampsia, and preterm in pregnant women with chronic HT, this was not the case in women with preeclampsia risk and obesity.

Based on the rarity of evidence, it is too early to make any conclusion given the limitation in the sample size of the studies, the difference in study design, outcome measurement, the timing

and duration of CPAP administration, and characters of subjects included. However, there are some important conclusions that we can make. First, despite the association of SDB and poor maternal and fetal outcomes shown in meta-analyses, there is not enough evidence from existing studies that CPAP treatment can improve pregnancy outcomes particularly, the reduction of preeclampsia and preterm labor. Second, there is no definite cut-off threshold for SDB diagnosis during pregnancy. Third, early and long-term CPAP treatment initiating during 1st trimester seemed more promising than in late pregnancy in improvement of pregnancy outcome. And lastly, in pre-eclamptic women during late pregnancy there is no evidence that CPAP can modify the disease progression, although 1-night CPAP might lower nocturnal blood pressure.

Hence, SDB pose a significant threat to pregnancy and fetus, diagnosis and treatment of SDB during pregnancy are still challenging given the dynamic changes of pregnancy and SDB. Because of the lack of evidence for the diagnostic and treatment threshold for SDB during pregnancy, there is currently no standard guideline to systematically screen and treat for SDB during pregnancy. The situation of SDB during pregnancy is in state of “clinical equipoise”, where the scientific community needs a strong evidence to make any treatment recommendation for the care of pregnant women at risk. It is an urgent need to conduct a randomized controlled trial that can demonstrate the efficacy of CPAP treatment in high risk pregnant women.

## **1.2 Research Question**

1.2.1 Does the use of CPAP treatment for SDB in pregnant women with preeclampsia risk result in better blood pressure control and thus reduce related maternal and fetal complications than standard usual antenatal care in control group

1.2.2 We want to investigate whether our proposed screening algorithm for SDB specific to pregnancy is accurate and feasible in monitoring and diagnosis of SDB during pregnancy.

### 1.3 Research Objectives

1.3.1 **Primary Objective:** To compare whether the treatment effect of CPAP on SDB during pregnancy can improve blood pressure control in high risk pregnancy

- Systolic/diastolic blood pressure during daytime ANC at 10:00-12:00 am at randomization (GA 0-16 week), 1.5-2 month after randomization (GA 18-20 week), and 3-4 month after randomization (GA 24-28 week), 5-6 month after randomization (GA 32-34 week) and monthly (GA>35 week) until delivery

1.3.2 **Secondary Objective:**

- To compare the composite outcome of pre-eclampsia/GHT, GDM, fetal growth restriction, and pre-term labor between the CPAP treatment and control groups. And individual outcomes.
- To compare the night-time blood pressure compared to control group. 2nd outcome

### 2.1 Definitions

**Obstructive sleep apnea (OSA)/Sleep disordered breathing (SDB)/Upper airway resistance syndrome (UARS):** Diagnostic criteria according to the International Classification of Sleep Disorders. 3rd Edition includes (A and B) or C satisfy the criteria [28]

A. The presence of 1 or more of the following:

1. The patients complain of sleepiness, nonrestorative sleep, fatigue, or insomnia symptom
2. The patient wakes with breath holding, gasping, or choking

3. The bed partner or other observer reports habitual snoring, breathing interruptions, or both during the patient's sleep.
4. The patient has been diagnosed with hypertension, a mood disorder, cognitive dysfunction, coronary artery disease, stroke, congestive heart failure, atrial fibrillation, or type 2 diabetes mellitus

B. PSG or out-of-center sleep test (OCST) demonstrates:

1. 5 or more predominantly obstructive respiratory events (obstructive and mixed apneas, hypopneas, or respiratory effort related arousal (RERAs) per hour of sleep during a PSG or per hour of monitoring (OSCT).

OR

C. PSG or OCST demonstrates:

1. 15 or more predominantly obstructive respiratory events (obstructive and mixed apneas, hypopneas, or respiratory effort related arousal (RERAs) per hour of sleep during a PSG or per hour of monitoring (OSCT).

**Apnea:** a reduction of thermistor signal at least 90% from baseline lasting for at least 10 seconds. Obstructive apnea is classified by the presence of RIP effort, and central apnea is classified by the absence of RIP effort [18].

**Hypopnea:** a reduction in nasal pressure transducer signal at least 30% from baseline that is associated with either O2 desaturation  $\geq$  3% from baseline or EEG arousal.

**Respiratory effort related arousals (RERA):** a sequence of breaths lasting  $\geq 10$  seconds characterized by increasing respiratory effort or by flattening of the inspiratory portion of the nasal pressure leading to arousal from sleep that does not meet the criteria for apnea or hypopnea.

**Apnea-hypopnea index (AHI):** = no. of apnea+hypopnea events/Total sleep time (hr)

**Respiratory disturbance index (RDI):** no. of apnea+hypopnea+RERA/Total sleep time (hr)

**Hypertensive disorder of pregnancy consisted of 4 categories [29]**

a) **Preeclampsia-eclampsia:** diagnostic criteria includes

▪ **Blood pressure:**

- $\geq 140/90$  mmHg on 2 occasions at least 4 hours apart after 20 weeks of gestation in a woman with a previously normal blood pressure
- $\geq 160/110$  mmHg, hypertension can be confirmed within a short interval (minutes) to facilitate timely antihypertensive therapy

And

▪ **Proteinuria**

- $\geq 300$  mg per 24-hour urine collection (or this amount extrapolated from a timed collection) OR
- Protein/creatinine ratio  $\geq 0.3$  (each measured as mg/dL)
- Dipstick reading of 1+ (used only if other quantitative methods not available)

Or in the absence of proteinuria, new-onset hypertension with the new onset of any of the following:

▪ **Thrombocytopenia**

- Platelet count <100,000/microliter
  - **Renal insufficiency**
    - Serum creatinine concentration > 1.1 mg/dL or a doubling of the serum creatinine concentration in the absence of other renal disease
  - **Impaired liver function**
    - Elevated blood concentrations of liver transaminases to twice normal concentration
  - **Pulmonary edema**
  - **Cerebral or visual symptoms**
- b) **Chronic hypertension (of any cause)** is hypertension that predates pregnancy
- c) **Chronic hypertension with superimposed preeclampsia** is chronic hypertension in association with preeclampsia
- d) **Gestational hypertension** is BP elevation after 20 weeks of gestation in the absence of proteinuria or the aforementioned systemic findings.

**Severe preeclampsia is defined with any of these findings:**

- $\geq 160/110$  mmHg on 2 occasions at least 4 hours apart while patient is on bed rest (unless antihypertensive therapy is initiated before this time)
- Thrombocytopenia (platelet counts <100,000/microliter)
- Impaired liver function as indicated by abnormally elevated blood concentrations of liver enzymes (to twice normal concentration), severe persistent right upper quadrant or epigastric pain unresponsive to medication and not accounted for by alternative diagnoses, or both

## Carpenter/Coustan

- Fasting 95 mg/dL
- 1-hour 180 mg/dL
- 2-hour 155 mg/dL
- 3-hour 140 mg/dL

HbA1C, fasting plasma glucose, 1-hour plasma glucose, 2-hour plasma glucose had been shown to be predictor of preeclampsia.

**Fetal growth restriction** is defined as a customized birthweight <10th centile for gestational age [31].

**Preterm labor is defined as** is the [birth](#) of a [baby](#) at less than 37 weeks [gestational age](#) [31, 32]

## 2.2 Conceptual framework

Conceptual framework is shown in figure 1

## 3. METHODOLOGY

### 3.1 Study design and setting

The study design will be a multicenter randomized-controlled trial in 3 tertiary care hospitals including Ramathibodi Hospital, Phramongkutklao Hospital and Rajavithi Hospital.

**3.1.1 Ramathibodi Hospital** is a [university hospital](#) of the Faculty of Medicine Ramathibodi Hospital which is a faculty within [Mahidol University](#) and the fourth oldest medical school in Thailand. The hospital serves at least 5,000 out-patient visits per day and in-patients with more

than 1,000 beds for tertiary medical care. The hospital provides approximately 3,000 antenatal care service and delivery each year. It will be the primary site of the research investigation. The study will initiate here in June 2016 and followed by other centers. The study will take approximately 2 years for the accrual time to achieve the target number of participants and another year for the completion and analysis.

**3.1.2 Phramongkutklao College of Medicine** is the first and only medical cadet school in [Thailand](#). The college is the seventh medical school established in Thailand by the will of [King Bhumibhol Adulyadej](#). Phramongkutklao College of Medicine is an affiliated college of [Mahidol University](#). It is the teaching hospital accommodating 1,200-bed in the tertiary level. The hospital provides approximately 3,000 antenatal care service and delivery each year. The research will start soon after the study initiation in Ramathibodi Hospital once the ethics committee and funding are approved. The study will take approximately 2 years for the accrual time to achieve the target number of participants and another year for the completion and analysis.

**3.1.3 Rajavithi Hospital** is a 1,200-bed medical center accommodating 40,000 in-patients and 1,000,000 out-patients yearly or a daily average of 4,000 patients, with 200,000 referral patients (both in and out patients). The hospital provides medical service at standard health promotion in tertiary levels and above, including quality referral system. The hospital provides approximately 4,000 antenatal care service and delivery each year. The research will start soon after the study initiation in Ramathibodi Hospital once the ethics committee and funding are approved. The study will take approximately 2 years for the accrual time to achieve the target number of participants and another year for the completion and analysis.

## 3.2 Study subjects

High risk pregnant women attending the antenatal care at the collaborated hospitals will be eligible for the study if they meet all following inclusion criteria.

### 3.2.1 Inclusion criteria (ALL criteria)

- Singleton pregnant women age  $\geq 18$  years without significant medical conditions such as immunocompromised status, chronic infection (HIV infection, tuberculosis), chronic lung and cardiac conditions, chronic kidney disease, thyroid disease, or neuromuscular disease.
- Pregnant women attending the 1st antenatal care and intending to deliver at one of the study hospitals with gestational age  $< 16$  weeks
- Thai nationality with ability to use Thai language proficiently both in spoken and written language.
- Have been diagnosed as high-risk pregnancy by obstetricians by having any of the following conditions
  - a. Chronic hypertension prior to pregnancy
  - b. Hypertension during pregnancy before 20week gestation.
  - c. Pre-eclampsia/gestational hypertension during recent pregnancy
  - d. Obesity defined by pre-pregnancy body mass index (BMI)  $\geq 27.5$  kg/m^2
  - e. Having diabetes mellitus or history of gestational diabetes in previous pregnancy
- Having SDB by either definition
  - a) RDI  $\geq 5$  events/hour by sleep testing at either point of testing during early pregnancy (0-16 GA week) or late pregnancy (GA 24-28 week)

- b) OR Presence of snoring (either as frequent snoring  $\geq 3$  times/week or loud snoring) prior to or occurring during pregnancy
- Sign written informed consent

### **3.2.2 Exclusion criteria**

- Subjects with severe obstructive sleep apnea (RDI  $\geq 30$  events/hour) or with significant O2 desaturation  $< 80\%$  during sleep that might have potential benefit from the CPAP treatment. CPAP treatment will be offered to these subjects.
- Subject with known obstructive sleep apnea and currently on CPAP treatment

Recruitment of subjects will be done at the antenatal care clinic. Screening for eligibility by investigators will be done, consecutively. Subjects who meet the inclusion criteria without any of the exclusion criteria will be approached to participate in the study.

### **3.3 Randomization and allocation**

A randomization list will be generated and stratified by collaborative center. For each stratum, a block randomization with varying block size from 4 to 8 will be performed using computerized program by STATA.

Preparation of randomization will be done by a third party, not involved in the clinical trial. The randomized code will be sealed into the sequentially numbered, opaque sealed envelopes (SNOSE) and send to each collaborative center. Investigators enrolling the patients will not be aware of the order of the randomization until opening the envelope for subject allocation.

### **3.4 Blinding**

This is an open-label randomized controlled trial, in which subjects will know each intervention she has received between CPAP machine and standard usual antenatal care. A blinded evaluation is planned to assess the observed primary and secondary end points by a separate outcome assessor.

### **3.5 Variable & measurement**

#### **3.5.1 Polysomnography (PSG)**

Screening for sleep disordered breathing (SDB) or obstructive sleep apnea (OSA) with either in-laboratory or home PSG will be performed depending on subject's preference. Performance of polysomnography will be done with SomnoTouchResp, which consisted of

- channels of electroencephalographies (EEG: F4M1, C4M1, O2M1)
- channels of electro-oculographies (EOG: ROC, LOC)
- Chin electromyography (EMG)
- Respiratory signals include nasal pressure transducer, oronasal thermistor, and pulse oximeter
- respiratory efforts using thoracic and abdominal respiratory inductance plethysmography (RIP)
- Sleep staging and respiratory scoring are according to the American Academy of Sleep Medicine 2012 version 2.2 [18]

1). Apnea is defined as a reduction of thermistor signal at least 90% from baseline lasting for at least 10 seconds. Obstructive apnea is classified by the presence of RIP effort, and central apnea is classified by the absence of RIP effort.

2). Hypopnea is defined as a reduction in nasal pressure transducer signal at least 30% from baseline that is associated with either O2 desaturation  $\geq$  3% from baseline or EEG arousal.

Apnea-hypopnea index is calculated as numbers of respiratory events per hour of total sleep time or recorded time.

3). Respiratory effort related arousal (RERA) is defined as a sequence of breaths lasting  $\geq$  10 seconds characterized by increasing respiratory effort or by flattening of the inspiratory portion of the nasal pressure leading to arousal from sleep that does not meet the criteria for apnea or hypopnea.

4). Additional scoring of airflow limitation and snoring time will be included as previously described [33].

Tabulation of respiratory index into apnea-hypopnea index [AHI] = no. of apnea+hypopnea/Total sleep time (hr)] and respiratory disturbance index [RDI =no. of apnea+hypopnea+RERA/Total sleep time (hr)] will be done.

### **3.5.2 Measurement of blood pressure**

- Measurement of blood pressure using manual sphygmomanometer during ANC visit will be done twice by research nurse in sitting resting position in non-dominant arm at least 15 minutes apart. Mean of the 2 values will used for the analysis.
- 24-hour blood pressure monitoring (ABPM) will be done
  - 24-hour BP monitoring device during daytime and night-time [34, 35] had been used in pregnancy population and showed good correlation with uterine artery Doppler ultrasound. “Non-dipping pattern” on the 24- hour

blood pressure monitoring had been shown can be to associated with preeclampsia and small for gestational age [36-39]. Validation of particular ABPM device is required based on the criteria set by the European Society of Hypertension position paper on ambulatory blood pressure monitoring [35]. The 24-hour BP monitoring in early pregnancy (GA<14 weeks) has been shown to predict occurrence of preeclampsia [40]. Furthermore, 24-hour SBP (per 10 mmHg [odd ratio(OR): 1.74; 95%CI:1.28-2.38; p<0.001]) was more closely associated with small-for-gestational age (SGA) than clinic BP (OR 1.40;95%CI:0.92-2.13; p=0.11) [41].

- Non-invasive blood pressure monitoring using the calculation from pulse transit time method (PTT). Validation of this device according to the European Society of Hypertension criteria had been done in non-pregnant population [42]. The device-observer disagreement was -0.44 6.1 mmHg for SBP and -0.33 3.4 mmHg for DBP. A strong correlation was observed between Somnotouch-NIBP and auscultatory method for SBP (r=0.973) and for DBP (r=0.976). The BP discrepancies did not vary according to sex (p>0.15), age, body weight, arm circumference (p>0.10). But a significant correlation was found between SBP discrepancy and height (r=0.4) [42].

### **3.5.3 Fetal ultrasound and Doppler ultrasound.**

Fetal ultrasound and Doppler ultrasound will be performed by experienced obstetrician to monitor parameters listed below [43]:

- Fetal growth by ultrasound: constant (above, below, or on curve); Falling off with increasing gestation (12 week, 18-20 week, 28 week, 36 week)

- Fetal hemodynamic including uterine, umbilical, and fetal middle cerebral artery blood flow indices at mid gestation (16-25 weeks) including 1) notching (yes/no): bilateral (yes/no); unilateral (yes/no); 2) pulsatility index (PI) and resistance index (RI). PI had been shown to be predictors of preeclampsia and intra-uterine fetal growth restriction [44, 45]. However, administration of methyl-dopa to lower blood pressure in preeclampsia showed no significant change after treatment [46, 48].
- Amount of amniotic fluid.

**3.5.4 Measurement of plasma glucose as described by 75-g OGTT.** HbA1C, fasting plasma glucose, 1-hour plasma glucose, 2-hour plasma glucose had been shown to be predictor of preeclampsia with odd ratio of 1.42 (1.33-1.52), 1.46(1.37-1.55), 1.40(1.32-1.50), 1.37(1.29-1.46), respectively [49].

### **3.6 Data collection**

#### **3.6.1 General management protocol for high risk women consisted of**

##### **3.6.1.1 During 1st trimester (First ANC, and subsequent 6-8 weeks ANC follow ups)**

- Clinical data collection such as demographic data, underlying disease, number of gestation, last menstrual period, height, pre-pregnancy weight, pregnancy weight, neck circumference, general physical examination, and systolic and diastolic blood pressure.
- Laboratory including fasting HbA1C, fasting blood sugar, complete blood count, serologic blood test (rubella titer, anti-HIV, VDRL, Rh blood group),
- Fetal ultrasound, uterine artery Doppler

### **3.6.1.2 Second trimester**

- Routine ultrasound at 18-20week gestation
- OGTT screening for GDM at 24-28week gestation
- 24-28week gestation: optional ultrasound depending on obstetrician's clinical decision
- Repeat blood test including fasting HbA1C, fasting blood sugar, complete blood count, and serologic blood test (anti-HIV, VDRL, Rh blood group)
- Urinary analysis

### **3.6.1.3 Third trimester**

- Bi-weekly to weekly ANC follow-ups until delivery
- Ultrasound at 32-34week gestational age

## **3.7 STUDY INTERVENTION**

### **3.7.1 CPAP intervention**

- Immediately after allocation, subjects in the intervention arm will receive CPAP treatment throughout pregnancy.
- Auto CPAP machine will be prescribed to subjects with pressure in the range of 4-15 cmH2O. Optimal pressure to eliminate respiratory events will be achieved based on the 90-95 percentile pressure.
- After determination with auto-CPAP, the machine with optimal pressure (range 4-15 cmH2O) adjustment will be prescribed. Subjects will be encouraged to use CPAP every night, continuously. Daily record of applying CPAP will be provided with SD card within the machine, which including the start and stop time start in CPAP usage.

- During subsequent trimester when reaching 24-28 weeks of gestation, another adjustment for optimal CPAP pressure will be determined with the auto-CPAP machine. In case if higher CPAP pressure is required, adjustment will be made accordingly.
- Data of CPAP usage and adherence will be automatically recorded in the machine and available for download during follow-up.

### **Control Group**

- Subjects will receive standard antenatal care and follow-up plan similar to the intervention group.

### **Primary outcome**

- Systolic and diastolic blood pressure, which will be measured at rest using sphygmomanometer twice by research nurses during daytime ANC at 10:00-12:00 am at randomization (GA 0-16 week), 1.5-2 month after randomization (GA 18-20 week), and 3-4 month after randomization (GA 24-28 week), 5-6 month after randomization (GA 32-34 week) and monthly (GA>35 week) until delivery

### **Secondary outcome**

- 24-hour ambulatory blood pressure monitoring (daytime versus night time) using the non-invasive technique from pulse transit time (SomnoTouch NIBP).
- Pregnancy complication listed as composite endpoints below

**(Composite endpoint):** A combination of clinical endpoints in maternal and fetal outcomes, data from Ramathibodi hospital during 2013-2014) \*

- **Composite 1:** hypertensive disorder of pregnancy or gestational diabetes; (composite1 incidence= $699/3787=18.5\%$ )
- **Composite 2:** hypertensive disorder of pregnancy or gestation diabetes or preterm labor or fetal growth restriction (composite 2 incidence = $812/3787= 21.4\%$ )
- **Composite 3:** Preterm labor or fetal growth restriction, or severe pre-eclampsia or eclampsia or death; (composite 3 incidence= $10\%$ )

\*Given that the incidence of hypertensive disorder incidence= $136/3787=3.6\%$ ; gestational diabetes incidence=  $601/3787=15.9\%$ ; fetal growth restriction incidence=  $157/3787=4.1\%$ ; preterm labor incidence= $10\%$ ; and severe pre-eclampsia/eclampsia/HELLP syndrome incidence= ( $43+ 1+3=46/3787=1.2\%$ ), respectively.

- Individual component of the composite endpoints including incidence of hypertensive disorder of pregnancy, gestational diabetes, preterm labor, and fetal growth restriction
- Glucose level, Oral Glucose Tolerance Test (OGTT), HbA1C
- Fetal ultrasound results: uterine Doppler arterial blood flow, fetal growth restriction
- Neonatal outcome: birth-weight, APGAR score, Length of stay, NICU admission
- Placenta character: weight will be measured at birth by the neonatal nurse.

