3.7.2 Control Group

- Subjects will receive standard antenatal care and follow-up plan similar to the intervention group.

Primary outcome

- Systolic and diastolic blood pressure, which will be measured at rest using sphygmomanometer twice on both arms by research nurses during daytime ANC at 10:00-12:00 pm at randomization (GA 0-16 week), 1.5-2 month after randomization (GA 18-20 week), and 3-4 month after randomization (GA 24-28 week), 5-6 month after randomization (GA 32-34 week) and monthly (GA>35 week) until delivery

Secondary outcome

- 24-hour ambulatory blood pressure monitoring (daytime versus night time) using the non-invasive technique from pulse transit time (SomnoTouch NIBP).
- Pregnancy complication listed as composite endpoints below

(Composite endpoint): A combination of clinical endpoints in maternal and fetal outcomes, data from Ramathibodi hospital during 2013-2014) *

- **Composite 1:** hypertensive disorder of pregnancy;
- **Composite 2:** hypertensive disorder of pregnancy or preterm labor or fetal growth restriction
- **Composite 3:** Preterm labor or fetal growth restriction, or severe pre-eclampsia or eclampsia or death; (composite 3 incidence=10%)

*Given that the incidence of hypertensive disorder incidence= $136/3787=3.6\%$;
gestational diabetes incidence= $601/3787=15.9\%$; fetal growth restriction incidence= $157/3787=4.1\%$; preterm labor incidence=10%; and severe pre-eclampsia/eclampsia/HELLP syndrome incidence= $(43+ 1+3=46/3787=1.2\%)$, respectively.

- Individual component of the composite endpoints including incidence of hypertensive disorder of pregnancy, gestational diabetes, preterm labor, and fetal growth restriction
- Glucose level, Oral Glucose Tolerance Test (OGTT), HbA1C
- Fetal ultrasound results: uterine Doppler arterial blood flow, fetal growth restriction
- Neonatal outcome: birth-weight, APGAR score, Length of stay, NICU admission

- Placenta character: weight will be measured at birth by the neonatal nurse.

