### **3.9.2 Based on composite endpoint**

Sample size calculation is also done according to the composite endpoint.

- **Composite 1** (hypertensive disorder of pregnancy or gestational diabetes)

For composite endpoint 1, sample size of 134 each arm is required to detect difference of 15% with type I and II error of 0.05 and 0.20 respectively. Therefore, given the sample size of 153 each arm from the primary endpoints, it is possible to include this composite endpoint.

- **Composite 2** (hypertensive disorder of pregnancy or gestation diabetes or preterm labor or fetal growth restriction or emergency C/S)

For composite endpoint 2, sample size of 141 each arm is required to detect the difference of 15% with type I and II error of 0.05 and 0.20 respectively. Therefore, given the sample size of 153 each arm from the primary endpoints, it is possible to include this composite endpoint.

And given the limitation in number of participant enrollment (n=306), estimation of the power of the study based on the effect size of the CPAP on composite endpoint 2 are done

below. To achieve a difference of 12% and 15% on the composite endpoint 2, given the sample size of 306, it will achieve the power of 0.83 and 0.97, respectively.

- **Composite 3**

For composite endpoint 3, sample size of 492 each arm is required to detect difference of 6% with type I and II error of 0.05 and 0.20 respectively. Therefore, given the sample size of 153 each arm from the primary endpoints, it is **Not** possible to include this composite endpoint.

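### The printed incidences of composites 2 and 3 are hard to reconcile with the component rates beside them, so the composite 2 powers of 0.83 and 0.97 lack a secure base and are probably, but not provably, too high for the definition that includes gestational diabetes.

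*Combined protocol and SAP*

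**What the plan says.** **Combined protocol and SAP, Secondary outcome.** The section gives incidences from one hospital's 2013–2014 records. Composite 1 (hypertensive disorder or gestational diabetes) is 699/3787 = 18.5%. Composite 2 is "hypertensive disorder of pregnancy or gestation diabetes or preterm labor or fetal growth restriction (composite 2 incidence" 812/3787 = 21.4%). Composite 3 is given as 10%. The footnote lists the components: hypertensive disorder 136/3787, gestational diabetes 601/3787, fetal growth restriction (FGR) 157/3787, preterm labor 10%, and severe pre-eclampsia/eclampsia/HELLP 46/3787. Preterm labor is the only component with no count.

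**Combined protocol and SAP, 3.9.2.** For differences of 12% and 15% on composite 2, "given the sample size of 306, it will achieve the power of 0.83 and 0.97, respectively". For composite 3, 492 per arm are required for a 6% difference, and the section concludes that this endpoint cannot be included.

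**Protocol, 3.7.2 and 3.9.2.** Gestational diabetes is removed from composites 1 and 2, and their incidences are no longer printed. The footnote still reads "preterm labor incidence=10%; and severe pre-eclampsia/eclampsia/HELLP syndrome incidence", again with no count for preterm labor. Composite 3 is unchanged: "Preterm labor or fetal growth restriction, or severe pre-eclampsia or eclampsia or death; (composite 3 incidence=10"%. The 3.9.2 powers of 0.83 and 0.97 and the 492 per arm are carried over.

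**The concern.** Composite 2 should exceed composite 1 by every woman who had a preterm birth or an FGR baby but neither hypertensive disorder nor gestational diabetes. With about 379 preterm births and 157 FGR babies among 3787 women, an excess of only 113 is surprisingly small. Composite 3 shows a similar pattern: a union of several components is printed at the rate of one of them.

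The control rate drives the stated power. For a fixed absolute fall, a higher control rate (below 50%) means a larger variance and lower power. If 21.4% is too low, a null result on composite 2 would be read as coming from a comparison with 83% power when the true figure may be nearer 70%.

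**Working it through.** **Inputs.** 699, 812, 157, 136 and 3787, 10% preterm, and 10% for composite 3 (Combined protocol and SAP, Secondary outcome); 153 per arm, absolute differences of 12 and 15 points, alpha 0.05 (3.9); two-sided tests (3.10.4).

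**1. Reproduce the stated powers.** With p1 the control rate, p2 = p1 − d, p̄ their mean and n = 153:

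power = Φ{[d√n − 1.96√(2p̄(1−p̄))] / √(p1(1−p1) + p2(1−p2))}

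- 21.4% vs 9.4%: 0.832
- 21.4% vs 6.4%: 0.970

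These are the printed 0.83 and 0.97. Working backwards with this formula, 0.83 implies a control rate of 21.3–21.7% and 0.97 implies 20.8–21.9%. The powers therefore rest on 21.4%.

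**2. Test 812 against the components.**

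- Added by preterm labor or FGR: 812 − 699 = 113.
- Preterm births, if the 10% applies to the same women: 0.10 × 3787 ≈ 379.
- Preterm births that must lie inside composite 1: at least 379 − 113 = 266, and 266/699 = 38%.
- Preterm rate in everyone else: at most 113/(3787 − 699) = 113/3088 = 3.7%.
- If the 10% is a rounded 9.5–10.5%, the minimum inside composite 1 is 247–284 women (35–41%).
- Even if all 136 hypertensive women delivered preterm, 266 − 136 = 130 of the 699 − 136 = 563 women with gestational diabetes only (23%) would also have to.
- FGR alone, if independent of composite 1, would add 157 × (1 − 699/3787) ≈ 128 women, close to 113.

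**3. Rate and power for composite 2 including gestational diabetes, at 153 per arm.**

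| Assumption | Control rate | Power, 12 points | Power, 15 points |
|---|---|---|---|
| Strict lower bound: preterm and FGR all within the 699 | 18.5% | 0.89 | 0.99 |
| As printed | 21.4% | 0.83 | 0.97 |
| 812 omits preterm, preterm independent: 1 − (1 − 812/3787) × 0.90 | 29.3% | 0.70 | 0.89 |
| Strict upper bound, no overlap: (699 + 379 + 157)/3787 | 32.6% | 0.66 | 0.86 |

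**4. Composite 2 without gestational diabetes (Protocol).**

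- Independence: 1 − (1 − 136/3787) × 0.90 × (1 − 157/3787) = 16.8%; powers 0.93 and above 0.99.
- No overlap: 3.6% + 10% + 4.1% = 17.7%; powers 0.91 and 0.99.
- Full nesting in preterm labor: 10%, from which a fall of 12 or 15 points is impossible.

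Emergency C/S, named in the 3.9.2 definition but not under Secondary outcome, has no printed rate and is left out here.

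**5. Composite 3.** A total of 10% equals preterm labor alone. Apart from rounding, it requires every FGR baby, severe case and death to be preterm. The severe counts 43 + 1 + 3 sum to 47, not 46 (1.2% either way). Independence gives 1 − 0.90 × (1 − 157/3787) × (1 − 47/3787) = 14.8%. With no overlap it is 15.4%. Deaths have no printed rate and are not counted. The two-proportion sample size for 10% vs 16% at 80% power is 492 per arm, so the printed 10% is the rate behind that figure.

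**The case against.** A reader might infer that preterm births were certainly left out and that 0.83 and 0.97 are therefore overstated. The documents do not support that much. The 812 lies inside the strict bounds (699 to about 1,235 women), and no overlap between components is printed. The 10% has neither numerator nor source; if it was not taken from the same 3787 records, the 812 may be sound and the powers stand for that definition. Nor do the component rates by themselves imply a range that excludes 21.4%. A narrower range needs an assumption about overlap.

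A reader might also carry the overstatement over to the Protocol, whose dates show it to be the later text. There the direction reverses. Without gestational diabetes, independence or no overlap gives a control rate below 21.4%, so the retained powers would be too low rather than too high, before any emergency C/S. Composite 3 cannot support a claim about 0.83 and 0.97 either, because its rate does not enter them, and the plan already says that it cannot power that endpoint.

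Finally, these are secondary endpoints, the trial's size rests on diastolic blood pressure, and the hospital-wide rates may not describe the trial's women. All of this stands and limits the consequence. It does not make the printed counts fit together or give the retained powers a basis.

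**Conclusion.** The figures need reconciling. For the Combined protocol and SAP, either preterm births are missing from the 812 or the 10% does not belong to these records; the split of 38% against 3.7% makes it implausible, though not impossible, that both are right. If preterm births were omitted and are independent of the other components, power falls from 0.83 to about 0.70 (12 points) and from 0.97 to about 0.89 (15 points). Within the strict bounds the powers are 0.66–0.89 and 0.86–0.99. Overstatement is thus likely but conditional.

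For the Protocol, the two powers have no printed incidence behind them. The printed components suggest about 0.91–0.93 and 0.99 under independence or no overlap, so the figures are stale rather than overstated. Composite 3's 10% is a separate doubtful figure that affects the 492 per arm. All powers here assume 153 per arm with complete outcomes, and hospital-wide rates as the control rate.

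**What to change.** Recount composites 2 and 3 woman by woman in the 2013–2014 records under the definitions that will be analysed, and state whether composite 2 includes emergency C/S. Print the numerator, denominator and source of the preterm rate, and correct the sum of the severe cases. Replace the incidences, then restate the 3.9.2 power sentence and the composite 3 sample size from the recount.

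If no recount is possible, replace the fixed 0.83 and 0.97 with the full bounds and label the independence value as an assumption. For composite 2 with gestational diabetes, the bounds are 18.5–32.6%, with powers 0.66–0.89 and 0.86–0.99. Without it, the components give 10–17.7% before any emergency C/S, with 16.8% under independence, and the text should say that falls of 12 or 15 points are not possible at the lower end.

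The cost is a short recount of records the sponsor's primary site should hold, a few changed figures, and less certain stated powers. Enrolment does not change.
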